## PROTOCOL AMENDMENT SUMMARY OF CHANGES TABLE

Document History		
Document	Date	Type of amendment
Original Protocol	02 Jul 2019	Not applicable

This document cannot be used to support any marketing authorization application and any extensions or variations thereof.

REDACTED COPY

---

# 1            **PROTOCOL SUMMARY**

## 1.1          **Synopsis**

### **Protocol title:**

An open-label, parallel-group, pharmacokinetic study of padsevonil in study participants with either normal hepatic function or with moderately impaired hepatic function (Child-Pugh Class B)

### **Short title:**

A pharmacokinetic, safety, and tolerability study of padsevonil in healthy study participants or those with moderate hepatic insufficiency

### **Rationale:**

Padsevonil (PSL) is currently being investigated for the treatment of focal-onset seizures in adult patients with drug-resistant epilepsy. Epilepsy is a disorder that increases significantly with age (Kilpatrick and Lowe, 2002). Impairment of renal and hepatic function is common in the elderly and may alter metabolism and excretion of a drug and its metabolites. Thus, PSL is likely to be administered in patients who have impaired hepatic function and, as a consequence, this may impact the efficiency of the study drug.

This study aims to evaluate the effect of moderate hepatic insufficiency on pharmacokinetic (PK), safety, and tolerability following single and multiple oral doses of PSL. Padsevonil is predominately cleared hepatically, and hepatic insufficiency may affect some pathways of hepatic/gut drug metabolism and has also been associated with other changes, such as changes in absorption, plasma protein binding, transport, and tissue distribution. As PSL is predominantly hepatically cleared, impairment of hepatic function anticipates increased exposures. These changes may be particularly prominent in patients with impaired hepatic function (CPMP/EWP/2339/02, 2005; Food and Drug Administration [FDA] Guidance for Industry, 2003).

## Objectives and endpoints

Objectives	Endpoints
Primary	

 
To evaluate the plasma PK of PSL in hepatically impaired and non-hepatically impaired study participants
 
	
 
Single dose: <math>C_{max}</math>, <math>AUC_{0-t}</math>, <math>AUC</math>
 
Multiple dose: <math>C_{max,ss}</math>, <math>AUC_{\tau}</math>
 

Secondary	

 
To evaluate the safety and tolerability of PSL in hepatically impaired and non-hepatically impaired study participants
 
	
 
Incidence of TEAEs, SAEs, and TEAEs leading to discontinuation
 

Other	

 
To evaluate plasma PK of PSL and its major metabolites (██████████) and (██████████) in hepatically impaired and non-hepatically impaired study participants
 
	
For PSL metabolites:
 
 
Single dose: <math>AUC</math>, <math>AUC_{0-t}</math>, and <math>C_{max}</math>
 
Multiple dose: <math>AUC_{\tau}</math> and <math>C_{max,ss}</math>
 
 
For PSL and its metabolites:
 
 
Single dose: <math>t_{max}</math>, <math>t_{1/2}</math>, <math>AUC_{0-12}</math>, and metabolic ratios of <math>AUC</math> and <math>C_{max}</math>
 
Multiple dose: <math>t_{max}</math>, <math>t_{1/2, ss}</math>, <math>C_{trough}</math>, metabolic ratios of <math>AUC_{\tau}</math> and <math>C_{max,ss}</math>
 
 
For PSL:
 
 
Single dose: <math>CL/F</math>
 
Multiple dose: <math>CL_{ss}/F</math>
 
Bound and unbound plasma concentration of PSL in 2 samples.
 

 
To evaluate the urine PK of PSL and its major metabolites (██████████) and (██████████) in hepatically impaired and non-hepatically impaired study participants
 
	
 
Amount excreted and metabolic ratio of amount excreted, <math>CL_R</math>, and <math>f_e</math>
 


 
To evaluate the safety and tolerability of PSL in hepatically impaired and non-hepatically impaired study participants
 
	
 
Changes in safety laboratory data (hematology, clinical chemistry, and urinalysis)
 
Changes in vital signs (PR, BP, RR, and body temperature)
 
Changes in 12-lead ECG assessment
 
Physical examination findings
 

BP=blood pressure; ECG=electrocardiogram; PK=pharmacokinetic(s); PSL=padsevonil; PR=pulse rate; RR=respiratory rate; SAE=serious adverse event; TEAE=treatment-emergent adverse event

## Overall design

This is a Phase 1, open-label study to evaluate the effect of moderate hepatic insufficiency on PK, safety, and tolerability following single and multiple oral doses of PSL.

The study includes a total of up to 24 study participants (Cohort A [approximately 12 participants] with normal hepatic function, and Cohort B [approximately 12 participants] with moderate hepatic insufficiency).

All cohorts will be initially matched for gender and then subsequently by weight to allow comparison across cohorts, if feasible. In each group there will be a homogenous repartition between male and female study participants with at least 2 study participants per gender.

Screening of study participants will be up to 28 days prior to entry into the clinic. Prior to the start of the open-label, Single-Dose Treatment Period, the participants will check in to the clinic and complete Baseline procedures and assessments preceding the first administration of study medication. This will then be followed by a Washout Period before the start of a Multiple-Dose Treatment Period. A second Washout Period will be undertaken before the participants have their End of Study (EOS) Visit. Please see the Schedule of Activities ([Table 1-3](#)) for more specific details.

### Number of participants

Up to 24 study participants will be enrolled overall. Approximately 12 study participants per cohort will be included. Dropouts will be replaced at the discretion of the Investigator and Sponsor.

### Treatment groups and duration

The maximum total duration for the study participants is 46 days; it will consist of a Screening Period, Baseline, 2 Treatment Periods, 2 Washout Periods, and an EOS Visit.

## 1.2 Schema

A table of criteria to define Child-Pugh score along with classification for hepatic insufficiency is presented in [Table 1-1](#). For those participants with hepatic insufficiency, only study participants classified as moderate with a Child-Pugh score of 7 to 9 inclusive will be enrolled. A detailed schematic diagram of the study is provided in [Table 1-2](#).

**Table 1-1: Criteria to determine Child-Pugh score**

Measure	1 Point	2 Points	3 Points
Total serum bilirubin (mg/dL)	<2.0	2.0 to 3.0	>3.0
Serum albumin (g/dL)	>3.5	2.8 to 3.5	<2.8
Prothrombin time (sec prolonged), OR INR (ratio)	<4 <1.70	4 to 6 1.70 to 2.30	>6 >2.30
Ascites	Absent	Slight	Moderate or participant is on medication(s) to control ascites
Hepatic encephalopathy	None	Grade 1 or 2	Grade 3 or 4 or participant is on medication(s) to prevent encephalopathy

Total points	Hepatic insufficiency classification
5 to 6	A-Mild
7 to 9	B-Moderate
10 to 15	C-Severe

INR=international normalized ratio

**Table 1-2: Study design**

Cohort A (Healthy Study Participants) and Cohort B (Child-Pugh Hepatic Insufficiency Classification of Moderate) (n=approximately 12 per cohort)											
	Single Dose			Multiple Dose							EOS/ETV
	Treatment Period	Washout Period		Treatment Period					Washout Period		
Day	1	2 to 5	6 to 7	8	9	10	11	12 (AM)	12 (PM)	13 to 17	18
PSL Dose (mg)	100 AM only			100 BID	100 BID	100 BID	100 BID	100 AM only			
Blood Sample	PK	PK (each day)		PK	PK	PK	PK	PK	PK	PK (until Day 17)	
Urine Sample	PK	PK (each day)						PK			

BID=twice daily; EOS=End of Study; ETV=Early Termination Visit; PK=pharmacokinetic; PSL=padsevonil

### **1.3 Schedule of Activities**

The Schedule of Activities is presented in [Table 1-3](#).

This document cannot be used to support any marketing authorization application and any extensions or variations thereof.

REDACTED COPY

**Table 1-3: Schedule of activities**

Procedures	Screening	Baseline		Single Dose			Multiple Dose					EOS a ETV	
		Treatment Period	Washout Period	Treatment Period	Washout Period	Treatment Period	Washout Period						
Study Days	-28 to -3	-2	-1	1	2 to 5	6 to 7	8	9	10	11	12	13 to 17	18
Written informed consent	X												
Admit to clinic		X b	X										
Demographics and baseline characteristics	X		X										
Inclusion/Exclusion criteria verification	X		X										
General medical/medications/procedures history	X		X										
Participant identification card assigned			X										
Determination of the Child-Pugh class	X												
Suicidality Risk Assessment (C-SSRS) c	X		X								X		X
Physical examination d	X		X								X		X
Psychiatric and mental status evaluation	X		X	X	X	X	X	X	X	X	X	X	X
Vital signs e	X		X	X	X	X	X	X	X	X	X	X	X
Pregnancy test f	X		X										X

**Table 1-3: Schedule of activities**

Procedures	Screening	Baseline		Single Dose			Multiple Dose					EOS a ETV	
		Treatment Period	Washout Period	Washout Period	Treatment Period					Washout Period			
Study Days	-28 to -3	-2	-1	1	2 to 5	6 to 7	8	9	10	11	12	13 to 17	18
Determination of the prothrombin and INR values	X												
Hematology, serum chemistry, urinalysis g	X		X				X				X		X
Serology (HIV, HepB and HepC)	X												
12-lead ECG h	X		X	X			X	X	X	X	X		X
Urine and cotinine drug screen, and alcohol breath test	X		X										
Recording of adverse events/medical procedures	X		X	X	X	X	X	X	X	X	X	X	X
Administer PSL				X			X	X	X	X	X		
Study drug accountability				X			X	X	X	X	X		
Blood sampling for PSL PK levels i				X	X		X	X	X	X	X	X	
Additional blood sample PPB j											X		
Urine collection for PSL PK k				X	X						X		

**Table 1-3: Schedule of activities**

Procedures	Single Dose			Multiple Dose								EOS a ETV	
	Screening	Baseline	Treatment Period	Washout Period	Treatment Period					Washout Period			
Study Days	-28 to -3	-2	-1	1	2 to 5	6 to 7	8	9	10	11	12	13 to 17	18
Discharge from clinic													X

CBC=complete blood count; C-SSRS=Columbia Suicide Severity Rating Scale; ECG=electrocardiogram; EOS=End of Study; ETV=Early Termination Visit; h=hour(s); Hep B=hepatitis B; Hep C=hepatitis C; HIV=human immunodeficiency virus; INR=international normalized ratio; PK=pharmacokinetic; PPB=plasma protein binding; PSL=padsevonil; WOCBP=women of childbearing potential

- a If a participant discontinues early, EOS procedures should be completed as the ETV. Upon early termination/withdrawal, the study participant will be encouraged to complete the Washout Period and complete EOS assessments following the last dose of study medication.
- b For convenience, the study participant may check-in to the clinic on the evening of Day -2. No study procedures will take place on Day -2. Study participants will be confined to the clinic from the time of check-in until check-out on Day 18.
- c All study participants will complete the “Screening/Baseline” version of the C-SSRS during Screening (assessing the past 6 months) and Baseline (Day -1), followed by the “Since Last Visit” version at subsequent visits.
- d Complete physical examinations will be performed on the days indicated. A brief physical examination will be conducted in a symptom-directed manner and only if clinically indicated (Section 8.4.1).
- e Vital signs will be performed before each morning dose of PSL, and if feasible, at the same times as ECGs are performed.
- f A serum pregnancy test will be performed for each WOCBP at Screening and a urine pregnancy test will be performed at any subsequent time points.
- g Laboratory safety assessments (hematology, chemistry, and urinalysis) will be performed before the morning dose of PSL.
- h A 12-lead ECG will be performed after a rest of at least 5 minutes. All ECG recordings will be performed in triplicate and should be sufficiently separated so they have a different ‘minute’ on the timestamp, and all are done within 4 minutes.
- i Pharmacokinetic blood samples will be taken at the following time points: Predose and 15 minutes, 30 minutes, 45 minutes, 1h, 1.5h, 3h, 4h, 5h, 6h, 8h, 12h, 24h (Day 2), 48h (Day 3), 72h (Day 4), and 96h (Day 5) postdose. On Days 8, 9, 10, and 11, PK samples will be taken at predose. On Day 12, PK blood samples will be taken at the following time points: predose and 15 minutes, 30 minutes, 45 minutes, 1h, 1.5h, 3h, 4h, 5h, 6h, 8h, 12h, 24h (Day 13), 48h (Day 14), 72h (Day 15), and 96h (Day 16) postdose.
- j Two blood samples will be collected after multiple doses at steady state (Day 12 predose and 1.5h postdose [ $\sim t_{max}$ ]) for PPB.
- k Urine for PK assessment will be collected from all study participants on Day 1 at predose and from 0h to <12h and 12h to <24h, on Day 2 from 24h to <48h, on Day 3 from 48h to <72h, on Day 4 from 72h to <96h, (before the 8am cutoff on Day 5) postdose. Urine for PK assessment will also be collected from all study participants on Day 12 from 0h to <12h postdose.

## 2 INTRODUCTION

### 2.1 Study rationale

Padsevonil is a novel chemical entity with selective affinity for both presynaptic vesicle protein 2 (SV2) isoforms and postsynaptic central benzodiazepine receptor (cBZR) sites on the gamma-aminobutyric acid type A (GABAA) receptor that has shown compelling, broad-range efficacy in several preclinical models of epilepsy conducted by UCB. Padsevonil is cleared via metabolism involving the cytochrome (CYP) pathway; the formation of the 2 major metabolites, [REDACTED] and [REDACTED], is mainly mediated by CYP3A4, with potential involvement of CYP2C19. Padsevonil is currently being investigated for the treatment of focal onset seizures in adult patients with drug-resistant epilepsy. Epilepsy is a disorder that increases significantly with age (Kilpatrick and Lowe, 2002). Impairment of renal and hepatic function is common in the elderly and may alter metabolism and excretion of a drug and its metabolites. Thus, PSL is likely to be administered in patients also with hepatic insufficiency.

Hepatic impairment can adversely affect some pathways of hepatic and gut drug metabolism and has also been associated with changes in absorption, plasma protein binding, transport, and tissue distribution. As PSL is predominately cleared hepatically, changes in these absorption, distribution, metabolism, and excretion aspects may be expected in study participants with impaired hepatic function (CPMP/EWP/2339/02, 2005; FDA Guidance for Industry, 2003).

Therefore, UP0056 is designed to evaluate the effect of moderate hepatic insufficiency on the PK, safety, and tolerability of PSL given orally either as a single dose or multiple doses.

### 2.2 Background

More than 50 million people worldwide experience epilepsy (World Health Organization [WHO], 2018). An imbalance between excitatory and inhibitory neurotransmission is widely recognized as a key factor leading to epilepsy. Consequently, drugs currently used in the treatment of epilepsy aim to restore this balance. In fact, most of the current antiepileptic drugs (AEDs) modulate neuronal transmission by either blocking voltage-gated sodium channels or acting on inhibitory/excitatory receptors located at the postsynaptic level.

The GABAA receptor mediates the bulk of inhibitory neurotransmissions in the brain. Allosteric modulation of inhibitory GABAA receptors by the cBZR site offers robust protection against seizures (Riss et al, 2008). However, their clinical use as AEDs is limited due to an unfavorable side effect profile (eg, drowsiness, ataxia, amnesia, paradoxical aggression), as well as the development of tolerance to anticonvulsant effects.

Compounds binding to SV2A proteins on synaptic vesicles are characterized by broad-spectrum efficacy against both generalized and partial seizures in preclinical models, and this protective activity strongly correlates with their binding affinity (Kaminski et al, 2008). The function of SV2B and SV2C subtypes is not well established, but they share a high degree of sequence homology to SV2A and localization within synaptic vesicles (Wan et al, 2010; Janz and Südhof, 1999). Levetiracetam (LEV), exemplifying a SV2A-related mechanism of action, displays prominent clinical efficacy in patients with different forms of epilepsy (Klitgaard and Verdru, 2007).

Compounds with dual activity at SV2A and GABAA receptors are expected to have superior efficacy to those drugs working through only one of these mechanisms. Preclinical data in animal models of epilepsy support this assumption with compelling synergistic interaction observed between LEV and AEDs with GABAergic mechanisms of action (Kaminski et al, 2009). This synergistic interaction was particularly pronounced when combinations of LEV and benzodiazepines were tested and a significant increase in the anticonvulsant potency of these drugs was observed associated with a higher therapeutic index.

Padsevonil is a novel chemical entity with selective affinity for both presynaptic SV2 proteins and postsynaptic cBZR sites on the GABAA receptor. At presynaptic sites, PSL binds with high affinity to all 3 subtypes of the SV2 protein (ie, SV2A, SV2B, and SV2C), and with moderate affinity to postsynaptic cBZR sites. Pharmacological results obtained in rodent models of either partial or generalized seizures in humans show that PSL provides potent and efficacious seizure suppression, suggesting a broad spectrum profile. Furthermore, PSL revealed potent and efficacious seizure suppression in models of drug-refractory epilepsy, suggesting superior efficacy against seizures refractory to currently used AEDs. Specifically, in the rat amygdala kindling model, a model of refractory focal epilepsy, PSL was the only compound that produced seizure freedom at doses that can be administered in humans. Valproate, brivaracetam, clonazepam, diazepam, and phenobarbital only produced seizure freedom at plasma exposures that exceeded the maximum human exposures multiple times over. Padsevonil is not associated with loss of anticonvulsant efficacy after repeated administration in mice, suggesting reduced potential for the development of tolerance. Because of its unique properties, PSL is currently being proposed as adjunctive therapy in the treatment of focal-onset seizures in adult patients with drug-resistant epilepsy.

Despite the occurrence of several electrocardiogram (ECG) findings (including different types of ectopy) both in healthy study participants and study participants with epilepsy, an independent expert cardiologist reviewed data from Phase 1 and Phase 2 studies and determined that none of these findings were assessed as being likely to be related to PSL. No clinically significant echocardiographic findings (only minor/trace or Grade 1 findings) have been observed in initial clinical efficacy studies, and all echocardiograms were assessed as normal. There are currently no clinical data to suggest that the drug has an adverse effect on cardiovascular function other than a minimal lowering effect on blood pressure (BP). The degrees of reduction seen in both systolic blood pressure (SBP) and diastolic blood pressure (DBP) are consistent with the GABAA-targeted mechanism of action of PSL and do not appear likely to have a clinically significant effect in therapeutic use. As a precaution, and in view of the nonclinical histopathological cardiac findings, echocardiogram screening of study participants at Baseline and ongoing echocardiogram monitoring during treatment and post-treatment have been implemented in the studies that have a >3-week treatment duration. To date, no clinically significant echocardiogram findings (only minor/trace or Grade 1 findings) have been observed.

More detailed information about the known and expected benefits and risks and reasonably expected AEs of PSL may be found in the Investigator's Brochure (IB). The current IB reflects the safety profile of PSL as it is known and may change with the accumulation of additional data.

The study participants (healthy participants and those with moderate hepatic insufficiency) included in this study will receive no medical benefit from participation. The risks from taking part in the study will be minimized through the selection of appropriate dose levels, selection of appropriate study participants defined by the inclusion/exclusion criteria, and safety monitoring.

### 3 OBJECTIVES AND ENDPOINTS

The objectives and corresponding endpoints for this study are presented in [Table 3-1](#).

**Table 3-1: Objectives and endpoints**

Objectives	Endpoints
Primary	

 
To evaluate the plasma PK of PSL in hepatically impaired and non-hepatically impaired study participants
 
	
 
Single dose: <math>C_{max}</math>, <math>AUC_{0-t}</math>, <math>AUC</math>
 
Multiple dose: <math>C_{max,ss}</math>, <math>AUC_{\tau}</math>
 

Secondary	

 
To evaluate the safety and tolerability of PSL in hepatically impaired and non-hepatically impaired study participants
 
	
 
Incidence of TEAEs, SAEs, and TEAEs leading to discontinuation
 

Other	

 
To evaluate plasma PK of PSL and its major metabolites [REDACTED] and [REDACTED] in hepatically impaired and non-hepatically impaired study participants
 
	
For PSL metabolites:
 
 
Single dose: <math>AUC</math>, <math>AUC_{0-t}</math>, and <math>C_{max}</math>
 
Multiple dose: <math>AUC_{\tau}</math> and <math>C_{max,ss}</math>
 
 
For PSL and its metabolites:
 
 
Single dose: <math>t_{max}</math>, <math>t_{1/2}</math>, <math>AUC_{0-12}</math>, and metabolic ratios of <math>AUC</math> and <math>C_{max}</math>
 
Multiple dose: <math>t_{max}</math>, <math>t_{1/2, ss}</math>, <math>C_{trough}</math>, metabolic ratios of <math>AUC_{\tau}</math> and <math>C_{max,ss}</math>
 
 
For PSL:
 
 
Single dose: <math>CL/F</math>
 
Multiple dose: <math>CL_{ss}/F</math>
 
Bound and unbound plasma concentration of PSL in 2 samples.
 

 
To evaluate the urine PK of PSL and its major metabolites [REDACTED] and [REDACTED] in hepatically impaired and non-hepatically impaired study participants
 
	
 
Amount excreted and metabolic ratio of amount excreted, <math>CL_R</math>, and <math>f_e</math>
 


 
To evaluate the safety and tolerability of PSL in hepatically impaired and non-hepatically impaired study participants
 
	
 
Changes in safety laboratory data (hematology, clinical chemistry, and urinalysis)
 
Changes in vital signs (PR, BP, RR, and body temperature)
 
Changes in 12-lead ECG assessment
 
Physical examination findings
 

BP=blood pressure; ECG=electrocardiogram; PK=pharmacokinetic(s); PSL=padsevonil; PR=pulse rate;  
RR=respiratory rate; SAE=serious adverse event; TEAE=treatment-emergent adverse event

## 4 STUDY DESIGN

### 4.1 Overall design

This is a Phase 1, open-label study to evaluate the effect of moderate hepatic insufficiency on PK, safety, and tolerability following single and multiple oral doses of PSL. The study design is shown in [Table 1-2](#).

A study participant who provides written informed consent will be screened within 28 days of first Treatment Period. Baseline procedures will be performed within 1 day of the first Treatment Period. Study participants will be included in a single- and multiple-dose study of PSL. The study will include up to 24 study participants divided into 2 cohorts (Cohort A [approximately 12 participants] with no hepatic insufficiency and Cohort B [approximately 12 participants] with Child-Pugh classified moderate hepatic insufficiency).

Both cohorts will be initially matched for gender and then subsequently by weight to allow comparison across cohorts, if feasible. Hepatically impaired participants will be recruited first and subsequent sexes and weight matched controls will be included, if feasible. In each group there will be a homogenous repartition between male and female study participants with at least 2 study participants per gender.

All activities will be completed as per the Schedule of Activities ([Table 1-3](#)). Screening and Baseline assessments will be followed by the Single-Dose Treatment Period and a Washout Period before entering the Multiple-Dose Treatment Period. The participants will then then undergo a second Washout Period before completing the EOS Visit.

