##### **Inclusion criteria for ALL study participants**

1. Participant must be male or female 18 to 70 years of age, inclusive, at the time of signing the informed consent.
2. Participant must have body weight of at least 50kg (males) or 45kg (females) and body mass index within the range 18 to 38kg/m^2 (inclusive).
3. Participant must be capable of giving signed informed consent as described in Appendix 1 (Section 10.1), which includes compliance with the requirements and restrictions listed in the informed consent form (ICF) and in this protocol.
4. Participant must be considered reliable and capable of adhering to the protocol, according to the judgment of the Investigator, and must be capable of communicating satisfactorily with the Investigator.
5. Participants must meet the following requirements to be included in the study:
  - A male participant must agree to use contraception as detailed in Appendix 4 (Section 10.4) of this protocol during both Treatment Periods and for at least 7 days after the last dose of study medication and refrain from donating sperm during this period.
  - A female participant is eligible to participate if she is not pregnant (see Appendix 4; Section 10.4), not breastfeeding, and at least 1 of the following conditions applies:
    - Not a woman of childbearing potential (WOCBP) as defined in Appendix 4 (Section 10.4)

OR

A WOCBP who agrees to follow the contraceptive guidance in Appendix 4 (Section 10.4) during both Treatment Periods and for at least 90 days (or 5 terminal half-lives) after the final dose of study medication.

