### **Specific inclusion criteria for study participants WITHOUT hepatic insufficiency**

6. Participants must be healthy as determined by medical evaluation, including medical history, physical examination, laboratory tests, and cardiac monitoring.

Note: Participant has clinical laboratory test results within the local reference ranges or values that are considered not clinically relevant by the Investigator and approved by the UCB Study Physician. Laboratory parameters outside the reference ranges can be retested, and if the retest result is within the reference range or considered clinically not relevant, the study participant will be allowed in the study.

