2.2 Study design and conduct

This is a Phase 1, open-label study to evaluate the effect of moderate hepatic insufficiency on PK, safety, and tolerability following single and multiple oral doses of PSL. The study includes a total of up to 24 study participants (Cohort A [approximately 12 participants] healthy participants, and Cohort B [approximately 12 participants] participants with moderate hepatic impairment).

All cohorts will be initially matched for gender and then subsequently by weight to allow comparison across cohorts, if feasible. In each group there will be a homogenous repartition between male and female study participants with at least 2 study participants per gender.

A table of criteria to define Child-Pugh score along with classification for hepatic insufficiency is presented in [Table 2-2](#). For those participants with hepatic insufficiency, only study participants classified as moderate, with a Child-Pugh score of 7 to 9 inclusive, will be enrolled.

The study utilizes a single dose (SD) and a multiple dose (MD) design. Screening of study participants will be up to 28 days prior to entry into the clinic. Prior to the start of the open-label, Single-Dose treatment period, the participants will check in to the clinic and complete Baseline procedures and assessments preceding the first administration of study medication. This will then be followed by a Washout Period before the start of a Multiple-Dose Treatment Period. A second Washout Period will be undertaken before the participants have their End of Study (EOS) Visit. Please see the Schedule of Activities (Table 2-3) for more specific details. Both healthy study participants and study participants with moderate hepatic impairment will take part in the Single Dose and Multiple Dose treatment periods.

The maximum total duration for the study participants is 46 days; it will consist of a Screening Period, Baseline, 2 Treatment Periods, 2 Washout Periods, and an EOS/ETV Visit.

Table 2.2: Criteria to determine Child-Pugh score

Measure	1 Point	2 Points	3 Points
Total serum bilirubin (mg/dL)	<2.0	2.0 to 3.0	>3.0
Serum albumin (g/dL)	>3.5	2.8 to 3.5	<2.8
Prothrombin time (sec prolonged), OR INR (ratio)	<4 <1.70	4 to 6 1.70 to 2.30	>6 >2.30
Ascites	Absent	Slight	Moderate or participant is on medication(s) to control ascites
Hepatic encephalopathy	None	Grade 1 or 2	Grade 3 or 4 or participant is on medication(s) to prevent encephalopathy

Total points	Hepatic insufficiency classification

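### Controls are matched on sex and weight but not on age, and no age adjustment is planned, so the primary exposure ratio is open to age confounding of unknown direction and size

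*Protocol*

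**What the plan says.** On matching, protocol section 4.1 reads "Both cohorts will be initially matched for gender and then subsequently by weight to allow comparison across cohorts, if feasible", and on the order of recruitment "Hepatically impaired participants will be recruited first and subsequent sexes and weight matched controls will be included, if feasible". The synopsis (protocol 1.1) carries the same rule, and SAP section 2.2 repeats it: "All cohorts will be initially matched for gender and then subsequently by weight to allow comparison across cohorts, if feasible". None of these names age.

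The first inclusion criterion, common to both cohorts, is "Participant must be male or female 18 to 70 years of age, inclusive". The controls have one further inclusion criterion: "Participants must be healthy as determined by medical evaluation".

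Protocol section 6.3 states that the study is open-label and not randomized. Protocol 9.3.1 and SAP 9.1 compare the cohorts by ANOVA on log-transformed parameters and report the ratio of geometric means with a two-sided 90% CI. SAP 4.1 (covariates) and SAP 4.10 (subgroups) are both marked not applicable. SAP 6.1 summarizes age by cohort descriptively. SAP 3.9, which lists changes from the protocol, adds nothing on age.

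The protocol's rationale links age with organ function: "Impairment of renal and hepatic function is common in the elderly and may alter metabolism and excretion of a drug and its metabolites".

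**The concern.** The study exists to isolate the effect of moderate hepatic insufficiency on padsevonil exposure. Without randomization, the two cohorts are comparable only on what is matched at recruitment or adjusted for in the model. The plan matches on two factors and adjusts for none.

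Age is an obvious candidate for a third. By the protocol's own account, older people more often have impaired organs, and impaired organs may handle drugs differently. The entry rules could also separate the cohorts in age. Controls must be healthy, with supine blood pressure up to 150/95 mmHg (exclusion 24) and largely without concomitant medication (section 6.5.1). Cohort B may have blood pressure up to 180/105 mmHg (exclusion 30) and may be allowed other chronic medication. That could favour younger controls, although the documents give no expected age for either cohort.

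If the mean ages differ and exposure depends on age, the planned ratio attributes the age effect to the liver. A site that follows the plan exactly could produce this, and nothing in the planned analysis would correct it.

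**Working it through.** **Inputs from the documents** (protocol 9.8, SAP 2.3): 12 per cohort, inter-participant CV 40%, log-normal AUC, ratio 2.0, one-sided alpha 0.05, two-sample t-test.

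**1. The plan's own figure.**
- SD on the log scale = sqrt(ln(1 + 0.40²)) = 0.3853; difference = ln 2 = 0.6931.
- SE of the log ratio = 0.3853 × sqrt(2/12) = 0.1573.
- Exact power with 22 df = 99.6%. The stated figure of more than 90% is reproduced. It does not bear on this point, which is about bias.
- Half-width factor of the planned 90% CI = exp(1.717 × 0.1573) = 1.31.

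**2. Bias from an age gap.** The documents give no age effect and no expected gap, so both are assumed. Let exposure rise by a fraction g per decade, and let Cohort B be older by a given gap in mean age. The impaired-to-healthy ratio is then multiplied by (1 + g)^(gap/10). The last column is the chance that the planned 90% CI lies wholly above 1 when hepatic impairment has no effect; with no age gap it is 5%.

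| Assumed rise per decade | Gap in mean age | Ratio multiplied by | True 2.0 appears as | CI wholly above 1, no liver effect |
|---|---|---|---|---|
| 3% | 10 years | 1.03 | 2.06 | 7% |
| 3% | 20 years | 1.06 | 2.12 | 10% |
| 5% | 10 years | 1.05 | 2.10 | 9% |
| 5% | 20 years | 1.10 | 2.21 | 15% |
| 10% | 10 years | 1.10 | 2.20 | 15% |
| 10% | 20 years | 1.21 | 2.42 | 32% |

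If Cohort B were the younger cohort, or if exposure fell with age, the bias would run the other way.

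**3. Can a model with age recover the comparison?** With age as a covariate, Var(log ratio) = SD² × (2/12 + gap²/(22 × ageSD²)), on 21 df. The within-cohort SD of age is assumed to be 10 to 15 years, and the residual SD is kept at 0.3853. For a 20-year gap and an age SD of 10: 2/12 + 400/2200 = 0.3485, SE = 0.3853 × sqrt(0.3485) = 0.2274, half-width factor = exp(1.721 × 0.2274) = 1.48.

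| Gap in mean age | Power for a ratio of 2.0 | 90% CI half-width factor |
|---|---|---|
| 0 | 99.6% | 1.31 |
| 10 years | 98.4 to 99.1% | 1.33 to 1.36 |
| 20 years | 90.4 to 96.8% | 1.39 to 1.48 |

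Under these assumptions an age-adjusted analysis is feasible with 12 per cohort. It loses precision as the gap grows, which is the reason to limit the gap at recruitment as well.

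**The case against.** The strongest reply is that the protocol never says padsevonil clearance depends on age. The rationale says organ impairment is more common in the elderly, and it does so to explain why impaired patients may receive the drug. The pathway it names is partly closed: an eGFR below 60 mL/min is excluded in both cohorts (exclusion 12), controls may not have liver disease (exclusion 27), and age is capped at 70. In Cohort B, hepatic impairment is the factor under study. What remains is an age effect apart from organ impairment, on which the documents are silent. All of this stands. It limits how strongly the point can be put, but none of these rules balances age between the cohorts.

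It is also fair that the likely size is modest. At 5% per decade and a gap of 10 to 20 years, the bias is about 5 to 10%, well inside the half-width factor of 1.31 and small beside a two-fold effect. The two-fold change is in any case only an input to an exploratory sample-size estimate, not a decision limit. Age will be summarized by cohort, so an imbalance would be visible, and the SAP introduction allows supplementary analyses after database lock. An analysis chosen after the imbalance is seen is weaker than one set in advance.

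A reader might infer three stronger things that the documents do not support:

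- That controls must be free of all hypertension and have bilirubin within normal limits, so that they are bound to be young. Exclusion 22 reaches only disorders that could materially affect drug handling, add risk or cloud the data. Exclusion 26 tolerates some isolated bilirubin elevation.
- That one extreme pair, such as a participant of 65 and a control of 22, shows the size of the bias. What matters is the gap in cohort means, and a 30-year gap would need means such as 55 and 25.
- That no later model could separate age from hepatic impairment. Step 3 of the working shows otherwise for gaps up to 20 years.

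**Conclusion.** The gap is real: age is neither matched nor adjusted for in a non-randomized comparison that admits participants from 18 to 70, so the primary ratio can mix age with hepatic impairment. Whether it will, and in which direction, cannot be settled from the documents. On the assumptions stated (exposure rising 3 to 10% per decade, Cohort B older), the ratio is multiplied by 1.03 to 1.10 at a 10-year gap and by 1.06 to 1.21 at a 20-year gap. The finding does not show that the ratio is biased, and it does not affect the stated power. It is a modest weakness in how clearly the result can be attributed to the liver, and it is worth closing because the remedy is cheap.

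**What to change.** 1. In protocol sections 1.1 and 4.1 and SAP section 2.2, add age as a third matching factor after sex and weight, where feasible. One form is to require the mean age of Cohort A to lie within a prespecified range of that of Cohort B. The width of the range is for the sponsor to set. Cohort B is recruited first and age is known at screening, so the target is available when controls are chosen.
2. Matching would still depend on feasibility, and an imbalance could remain. In SAP sections 4.1 and 9.1, therefore, prespecify a sensitivity ANCOVA of the log-transformed primary PK parameters with cohort as factor and age as covariate, reported beside the planned ANOVA.

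No extra assessment and no change of sample size is needed. The costs are somewhat slower recruitment of controls, possibly looser weight matching when a third factor competes for about 12 controls, and a wider 90% CI in the sensitivity analysis if ages differ. That analysis also relies on an age slope estimated from about 24 participants, which is why it should support the primary analysis and not replace it.
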